## **9.2 Safety Assessments**

### **9.2.1 Medical History**

A complete review of the patient's medical history will be undertaken by the Investigator or designee at the Screening visit (Visit 1) to ensure that no exclusion criteria have been met. Any concomitant disease, whether considered relevant for the study or not by the Investigator, must be reported in the CRF. The date of diagnosis or duration of the condition should be noted where possible.

### **9.2.2 Physical Examination**

A physical examination will be performed by the Investigator as per the Study Flow Chart (Appendix 1) at all visits in accordance with local practices. This examination will be symptom-directed, i.e., a standard panel of body systems will not be assessed unless indicated by patient. For example should the patient report to the Investigator the presence of 'rash' then the skin would be evaluated. It is not required that additional body systems are assessed unless clinically warranted. Any clinically significant abnormal results should be recorded in the CRF. Changes in findings of the physical examination compared with the baseline examination should be recorded as an AE.

### **9.2.3 Vital Signs**

Vital signs measurements will be performed as per the Study Flow Chart (Appendix 1) at every visit. Measurements to be taken include:

- Blood pressure: will be performed as supine (after at least 5 minutes of rest) systolic and diastolic blood pressure (in mmHg)

- Heart rate: taken at rest (in bpm)
- Temperature: will be taken as per clinic practice. Temperature and route will be recorded in the CRF.

Vital signs measurements will be performed before any blood samples are taken. All new findings or changes to previous findings considered clinically significant will be recorded in the CRF as an AE if the finding is made after the patient has signed the ICF.

#### 9.2.4 Clinical Laboratory Safety Tests: Haematology, Serum Biochemistry, and Urinalysis

Blood and urine samples will be taken as per the study flow chart (Appendix 1) for routine haematology, serum biochemistry and urinalysis tests. All samples will be analysed in the central laboratory.

**Table 2: Clinical Laboratory Safety Tests**

Haematology:	Full blood count to include red cell count, haemoglobin, haematocrit, white cell count, differential white cell count, platelet count.
Serum biochemistry:	Creatinine, uric acid, alkaline phosphatase (ALP), alanine aminotransferase (ALT), lactate dehydrogenase (LDH), creatine phosphokinase (CPK), albumin, cholesterol, triglycerides, glucose.
Urinalysis:	pH, protein, glucose, blood.

**Table 3: Total Blood Volume drawn**

Test	Number of Samples	Volume per sample (ml)	Total (ml)
Haematology/Biochemistry	4*	9	36
Biomarkers	2	3	6
Total volume			42

\*Sample at Visit 7/Follow up will only be taken if a laboratory AE was recorded at Week 8  
If required a follicle-stimulating hormone (FSH) test to confirm non-child bearing potential will be carried out at screening only.

Details of the volume of blood or urine to be taken, sample preparation and handling are contained in a separate Laboratory Procedures Manual. Laboratory results will be reviewed for clinically significant values by each Investigator following sample analysis and verification. The report must be initialled and signed by the Investigator before insertion in the CRF.

Additional blood may be required for repeats of safety laboratory test.

### **9.2.5 Pregnancy Test**

For female patients of childbearing potential, a pregnancy test will be carried out at screening, as per the study flow chart (Appendix 1).

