	
hepatitis C or infection with human immunodeficiency virus).
 
13. Patients with a history of clinically significant drug or alcohol abuse in the opinion of the Investigator in the last year prior to baseline (Day 0).
 
14. Patients who have participated in any other clinical study with an investigational drug within 3 months before the first day of administration of study treatment.
 
15. Patients who have had treatment with biologics as follows:
 

Any cell-depleting agents including but not limited to rituximab: within 6 months before the screening visit, or until lymphocyte count returns to normal, whichever is longer,

Other biologics influencing cell proliferation: within 6 months before the screening visit.

 
16. Patients who are pregnant, planning pregnancy, breastfeeding and/or are unwilling to use adequate contraception (as specified in inclusion criterion 7) during the trial.
 
17. Patients, in the opinion of the Investigator, not suitable to participate in the study.

TEST PRODUCT, DOSE AND MODE OF ADMINISTRATION:	
DS107 cream will be provided as a cream containing either 5% or 1% DS107.
 
Vehicle will be provided as a matching cream.
 
This study will involve two dose levels of DS107 for 8 weeks (5% DS107 cream BD or 1% DS107 cream BD) and a vehicle control BD.

EVALUATION CRITERIA: SAFETY	

Physical examination

Vital signs, including blood pressure (BP), pulse and temperature

Clinical laboratory tests (haematology, biochemistry, and urinalysis)

Pregnancy test for females of child bearing potential

AEs

Concomitant medications (CMs)

BEHAVIOURAL RESTRICTIONS	
 
Patients will be asked to refrain from any travel to sunny climates or use of tanning equipment, saunas and swimming throughout the duration of the study.
 
Extensive UV exposure or UV-B devices within four weeks of the trial and during the trial.
 

OTHER RESTRICTIONS	
 
Patients will be asked to refrain from the application of all emollients and creams to any area of skin impacted by AD during the course of this study.
 

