## 7 PATIENTS AND SCREENING

In order to participate in this study the patients must meet all of the following inclusion criteria (see section 7.2) and must not meet any of the following exclusion criteria (see section 7.3). Inclusion in the trial starts with the informed consent signature. The inclusion and exclusion criteria are to be verified at the screening visit (Visit 1) and at the start of treatment/baseline visit (Visit 2).

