### 7.3 Exclusion Criteria

1. Patients with other skin conditions that might interfere with AD diagnosis and/or evaluation (such as psoriasis or current active viral, bacterial and fungal topical skin infections) as assessed by the Investigator.
2. Patients who have used systemic treatments (other than biologics) that could affect AD less than 4 weeks prior to baseline visit (Day 0), e.g. retinoids, methotrexate, cyclosporine, hydroxycarbamide (hydroxyurea), azathioprine and oral/injectable corticosteroids. Intranasal corticosteroids and inhaled corticosteroids for stable medical conditions are allowed.
3. Patients who have used any topical medicated treatment for AD two weeks prior to start of treatment/baseline (Day 0) including but not limited to, topical corticosteroids, calcineurin inhibitors, tars, bleach, antimicrobials and bleach baths.
4. Patients who use topical products containing urea, ceramides or hyaluronic acid two weeks prior to Day 0.
5. Patients who use anti-histamines for AD within 3 days of baseline. Non-sedative anti-histamines for other indications may be used throughout the study provided the patient is on a stable dose for 4 weeks prior to baseline.
6. Patients who have had excessive sun exposure, have used tanning booths or other ultraviolet (UV) light sources four weeks prior to baseline (Day 0) and/or are planning a trip to a sunny climate or to use tanning booths or other UV sources between screening and follow-up visits.
7. Patients who have a history of hypersensitivity to any substance in DS107 or vehicle cream.
8. Patients who have a white cell count outside of the normal reference range at screening, which cannot be justified by the investigator.
9. Patients who have any clinically significant controlled or uncontrolled medical condition or laboratory abnormality that would, in the opinion of the Investigator, put the patient at undue risk or interfere with interpretation of study results.

---

10. Patients who have a clinically significant impairment of renal or hepatic function.
11. Patients with significant uncontrolled cardiovascular, neurologic, malignant, psychiatric, respiratory or hypertensive disease, as well as uncontrolled diabetes and floride arthritis or any other illness that, in the opinion of the Investigator, is likely to interfere with completion of the study.
12. Patients with chronic infectious diseases (e.g., hepatitis B, hepatitis C or infection with human immunodeficiency virus).

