## 8 STUDY CONDUCT

### 8.1 Study Schedule

During the study, six visits to the clinic are scheduled after the screening visit: one at the start of the comparative treatment period/Baseline (Day 0/Visit 2) and five in the comparative treatment period (Week 2/Visit 3, Week 4/Visit 4, Week 6/Visit 5, Week 8/Visit 6). A final safety follow-up visit (Visit 7) will be conducted two weeks after Visit 6 or two weeks after the final visit attended if the patient does not complete the study. The baseline visit must be performed, at the latest 30 days after the screening visit.

In the event that treatment is occurring, a wash out period of up to 4 weeks may be necessary. At the Screening visit, after giving informed consent to participate, patients will be assessed using the screening examinations. Eligible patients with confirmed AD using the Hanifin and Rajka criteria and who meet all the inclusion criteria and do not meet the exclusion criteria at the baseline visit will be enrolled.

During the treatment period and follow-up period patients will be restricted from using any other treatment for AD, or from taking new or not previously prescribed anti-histamines or any antimicrobial medication. Any medication (prescription as well as over the counter (OTC) drugs) or therapeutic intervention deemed necessary for the patient, and which in the opinion of the Investigator do not interfere with the safety and efficacy evaluations, may be continued. Emollients can be applied to other areas of dry skin not in the defined treatment area. A list of ‘medications and therapeutic regimens excluded from the study’ is defined below (Section 9.2.9).

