### **8.2.2 Treatment Period**

Following completion of a successful screening visit, patients will begin the comparative treatment period (8 weeks).

At the start of the comparative treatment period, after confirmation of continued eligibility, patients will be randomly assigned at the baseline visit (Visit 2) to one of the three treatment regimens.

Patients will be instructed to apply DS107 cream or vehicle cream in the morning and in the evening (except on the mornings of clinic visits when patients will be instructed to abstain from applying DS107/vehicle cream prior to the visit. They will apply DS107/vehicle cream as soon as all of the efficacy assessments are complete during the clinic visit). Each self-administration of IMP will be recorded in a patient compliance log.

Unscheduled visits may occur when a patient needs to make a visit in between the scheduled visit dates due to an AE, difficulty complying with the study protocol requirements, or a significant change in their disease state. All procedures that are medically necessary should be followed.

Patients who discontinue the study early will have all study procedures scheduled for Visit 6 (see Section 8.2.7) performed as soon as possible after patient withdrawal so that all study-related information can be recorded.

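### Pregnancy is tested only at screening, up to 30 days before randomisation and first application; add a site-read test at Visit 2

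*Protocol*

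**What the plan says.** Exclusion 16 bars "Patients who are pregnant, planning pregnancy, breastfeeding and/or are unwilling to use adequate contraception". Protocol Section 7 states: "The inclusion and exclusion criteria are to be verified at the screening visit (Visit 1) and at the start of treatment/baseline visit (Visit 2". Section 8.2.2 repeats the requirement for the day of randomisation: "after confirmation of continued eligibility, patients will be randomly assigned at the baseline visit (Visit 2". The Visit 2 list in Section 8.2.3 includes this verification.

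On testing, Section 9.2.5 says: "For female patients of childbearing potential, a pregnancy test will be carried out at screening, as per the study flow chart (Appendix 1". The Visit 1 list in Section 8.2.1 includes the sample, and the flow chart in Appendix 1 has one mark in the pregnancy-test row, under Screening. The Visit 2 list has no pregnancy test. The urinalysis panel in Table 2 is pH, protein, glucose and blood, so the urine taken at Visit 2 does not supply one. The first application is made on site at Visit 2.

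On timing, Section 8.1 says: "The baseline visit must be performed, at the latest 30 days after the screening visit". For patients on treatment it adds that "a wash out period of up to 4 weeks may be necessary". Exclusion 3 covers "Patients who have used any topical medicated treatment for AD two weeks prior to start of treatment/baseline (Day 0" and exclusion 2 covers "Patients who have used systemic treatments (other than biologics) that could affect AD less than 4 weeks prior to baseline visit (Day 0".

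**The concern.** Visit 2 has to confirm that a woman is not pregnant, but the only test evidence available there is the screening result. The rest of the check is history and contraception status. Other objective checks (haematology, biochemistry, urinalysis, vital signs) are refreshed at Visit 2; pregnancy status is not. The physical examination is symptom-directed (Section 9.2.2) and is no substitute.

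The delay is built into the schedule, because a washout that begins at screening forces one. A woman who conceives during it, or whose pregnancy was too early to show at screening, can be randomised and start treatment the same day. No test is scheduled after that either, so detection rests on the patient telling the site (Section 11.4) or on history at the two-weekly visits. What is at stake is avoidable exposure to study drug in pregnancy, followed by withdrawal from study drug and follow-up of the pregnancy to its outcome. The schedule sections agree with one another, so this is a gap in the schedule and not a contradiction.

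**Working it through.** **Age of the result at randomisation.** The inputs are the visit schedule (Section 8.1, Appendix 1) and the washout rules (Section 7.3).

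- Oldest permitted result: Day 0 minus Day -30 = 30 days, which reproduces the limit in Section 8.1.
- Youngest: Day 0 minus Day -1 = 1 day.
- Topical washout starting at screening: 2 × 7 = at least 14 days.
- Systemic washout starting at screening: 4 × 7 = about 28 days, which leaves 30 − 28 = 2 days of slack within the limit.
- With a Visit 2 test: 0 days.

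**Untested window before first application.** Let G be the gap from screening to Visit 2, and let d be the number of days after conception during which a test is still negative.

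- Screening test only: conceptions in the last G + d days go undetected.
- Visit 2 test added: conceptions in the last d days go undetected.
- Gain: (G + d) − d = G, whatever d is. G is 14 to 30 days for women who start a washout at screening and can be as short as 1 day for others.

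**Expected number of pregnancies.** The documents give neither the number of women of childbearing potential nor a pregnancy rate. I assume 100 to 150 women and 1 to 10 pregnancies per 100 woman-years, with every woman having a gap of 14 to 30 days.

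Count = women × annual rate × G/365.

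| | Women | Rate per year | G (days) | All arms | DS107 arms (× 2/3) |
|---|---|---|---|---|---|
| Low | 100 | 0.01 | 14 | 0.038 | 0.026 |
| High | 150 | 0.10 | 30 | 1.233 | 0.822 |

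The factor of two thirds follows from 1:1:1 allocation with two DS107 arms. If only a fraction of the women need a washout, their contribution falls in proportion. A woman with a 1-day gap adds almost nothing: 100 women at the low rate give 100 × 0.01 × 1/365 = 0.003.

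**The case against.** The strongest reply is that this is a preference about scheduling. Nothing in the protocol requires a test within a set time of dosing, and exclusion 16 is partly a matter for interview in any case (plans for pregnancy, willingness to use contraception). Inclusion 7 requires contraception throughout the study, and Section 7 dates inclusion in the trial from signature of the consent form, so the natural reading is that contraception already covers the washout. The minipig study in Section 1.5 found no significant systemic exposure from topical use, and the active ingredient is a fatty acid naturally present in the body (Section 1.3). Section 11.4 has a procedure for pregnancies that do occur.

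Much of this stands as a limit on the risk. Contraception from consent lowers the chance of conception during the washout, but it does not establish status on the day of dosing. Nor does it help with a pregnancy already present but undetectable at screening. Barrier methods and abstinence are accepted, and only hormonal methods have a stated lead-in before baseline. The animal data are reassuring, yet the protocol still excludes pregnant women and stops study drug when pregnancy is confirmed; the toxicology summary in Section 1.5 reports no reproductive study.

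The counts are also open to challenge. The high figure combines the most women, the highest rate and the longest gap for everyone, and it gives no credit to the history taken at Visit 2, which would find some of these pregnancies. It is best read as an upper value under the stated assumptions.

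**Conclusion.** The point holds, as a low-cost safety improvement to consider. The schedule facts are certain: one test at screening, a result up to 30 days old at randomisation, and a gap of at least 14 or about 28 days for any woman who starts a topical or systemic washout at screening. The size of the benefit is much less certain. Under the assumptions above it is 0.04 to 1.2 pregnancies over all arms (0.03 to 0.8 on DS107), and fewer if few women need a washout or if history at Visit 2 finds some of them. The case therefore rests on the consequence of a single missed pregnancy set against a very small cost. Sample size, power, type I error and the endpoints do not change.

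**What to change.** Make three edits to the protocol.

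1. In Section 9.2.5, add that the test is repeated as a urine test at Baseline/Visit 2 and read at site before randomisation, and that a positive result is a screen failure under exclusion 16.
2. In Section 8.2.3, list the test above the randomisation step.
3. In Appendix 1, mark the pregnancy-test row in the Baseline column.

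Specify that the strip is read at site. Section 9.2.4 sends the safety samples to the central laboratory, and Section 9.2.5 does not say where the pregnancy test is read. A result sent out from Visit 2 would probably arrive after same-day randomisation and first application.

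The cost is protocol wording and one strip per woman of childbearing potential, at a visit where urine is already collected, plus an occasional late screen failure. A further test at Visit 6 is optional. The last application is the day before that visit, so the test could not prevent exposure and would only make the reporting of on-treatment pregnancies more complete.

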### **9.2.6 Biomarker Sampling**

Blood samples will be collected via direct venepuncture as per the study flow chart (Appendix 1) at baseline/Visit 2 and Week 8/Visit 6/ET and will be stored for the potential analysis of AD biomarkers at a later date.

The detailed instruction for biomarker sample collection, processing, storage and shipment will be provided in a separate procedure.

### **9.2.7 Sample Storage, Handling and Shipping**

Sample storage, handling and shipping will be done as per standard operating procedures and as specified in the Laboratory Procedures Manual.

### **9.2.8 Adverse Event Assessment**

See Section 11.

### **9.2.9 Concomitant Medication**

Any medication (prescription as well as over the counter (OTC) drugs, vitamins and antacids) or therapeutic intervention deemed necessary for the patient, and which, in the opinion of the Investigator, does not interfere with the safety and efficacy evaluations, may be continued unless they are included in the list of ‘medications and therapeutic regimens excluded from the study’ outlined below. However, the Investigator should be cautious in evaluating the need for change in dosage and should carefully assess if any concomitant medication is necessary.

Any medications, herbal medicines, natural health remedies and nutritional supplements used within 30 days prior to screening (Visit 1) until completion (Visit 7) are to be recorded in the concomitant medication module in the CRF system. The generic name of the medication (i.e., not local trade names), along with start date, stop date, dose, route, regimen and indication shall be recorded as applicable in the CRF system.

---

Any new medications or changes to the dose or regimen of pre-existing medications will be updated on a routine basis during the study.

Investigational new drugs (i.e. drugs that are not marketed in the local market) should not be co-administered with the IMP during the entire period of the study.

#### **9.2.9.1 Permitted Therapies**

Non-sedative anti-histamines (e.g. loratadine, fexofenadine) are allowed during the study only if used to treat medical conditions other than AD. Such medications are allowed during the study only if the patient has been on a stable dose for at least 4 weeks prior to baseline/ Day 0 and continues to use the same agent everyday throughout the study

Inhaled and intranasal corticosteroids for stable medical conditions are allowed.

#### **9.2.9.2 Medications and Therapeutic Regimens Excluded From Use in the Study**

The following topical therapies or procedures are prohibited during the study for all patients:

- Topical medicated treatments that could affect AD, including but not limited to:
  - topical corticosteroids
  - calcineurin inhibitors
  - tars
  - bleach
  - antimicrobials
  - bleach baths
- Any topical product containing urea, ceramides or hyaluronic acid
- Emollients within the test area (may be applied to areas of dry skin outside of the test area and must be in use for 4 weeks prior to initiation of trial)
- Systemic therapy that could affect AD, e.g. retinoids, methotrexate, cyclosporine, hydroxycarbamide (hydroxyurea), azathioprine and oral/injectable corticosteroids
- Anti-histamines used for AD
- Any biological agent
- UVA or UVB phototherapy
- Psoralen + Ultraviolet A (PUVA) therapy
- Use of tanning booth
- Any other investigational medicinal product
- Traditional medicine, herbal extracts and supplements used to treat AD

### 9.2.10 Restrictions

#### Behavioural

Patients will be asked to refrain from any travel to sunny climates or use of tanning equipment, saunas and swimming throughout the duration of the study.

Extensive UV exposure or UV-B devices within 4 weeks of the trial and during the trial.

#### Other

Patients will be asked to refrain from the application of all emollients and creams to any area of skin impacted by AD during the course of this study.

Patients will be instructed to abstain from using any drugs/treatments that may influence AD (refer to exclusion criteria and prohibited therapies or procedures section) throughout the study.

## 10 INVESTIGATIONAL MEDICINAL PRODUCT / INVESTIGATIONAL DRUG

### 10.1 IMP

The following medication supplies will be used in the study:

#### DS107 cream:

DS107 cream contains DS107 as an active ingredient.

DS107 cream will be supplied in two concentrations: 5% and 1%.

DS107 cream is formulated as a white to off white-cream for topical application.

